## Protocol

---

**SYNOPSIS**

**Title of study:** TRK-250 – A Phase I, Double-Blind, Placebo-Controlled, Single and Multiple Inhaled Dose, Safety, Tolerability, and Pharmacokinetic Study of TRK-250 in Subjects with Idiopathic Pulmonary Fibrosis

**Objectives:**

The primary objective of the study is to assess the safety and tolerability of single and multiple inhaled doses of TRK-250 in subjects with idiopathic pulmonary fibrosis (IPF).

The secondary objective of the study is to assess the pharmacokinetics (PK) in blood following single and multiple inhaled doses of TRK-250 in subjects with IPF.

**Endpoints:**

The primary safety endpoints for this study are as follows:

- body weight
- vital signs measurements
- oxygen saturation (SpO2) by pulse oximetry
- hematology, clinical chemistry, and urinalysis test results
- 12-lead electrocardiogram (ECG) parameters
- forced expiratory volume over 1 second (FEV1), forced vital capacity (FVC)
- incidence and severity of adverse events (AE)

The single and multiple ascending dose PK outcome endpoints of TRK-250 are as follows (where applicable):

- area under the concentration-time curve (AUC) from time zero to the time of the last quantifiable concentration (AUC0-*t*last)
- maximum observed concentration (Cmax)
- time to Cmax (Tmax)

Other PK parameters may also be added.

**Study design:**

This will be a Phase I, double-blind, randomized, placebo-controlled study conducted in 2 parts, single and multiple inhaled dose, at multiple sites.

**Part A**

Part A will comprise a single-dose, single-period, sequential-cohort study. Potential subjects will be screened to assess their eligibility to enter the study within 28 days prior to study drug administration.

It is planned that 16 subjects will be studied in 4 cohorts (Cohorts A1 to A4), each consisting of 4 subjects. Following data monitoring committee (DMC) review of the safety and tolerability data from the first 4 cohorts, up to 3 further optional cohorts (Cohorts A5 to A7) of at least 4 subjects may be added to Part A to evaluate additional doses or to further evaluate planned doses.

**Investigational treatment and follow-up duration:**

The first 2 subjects to be dosed in each cohort of Part A will reside at the study site from Day 1 (the day of dosing) to Day 2 (24 hours post completion of dose administration). After Investigator review of the safety data through Day 2 from the first 2 subjects, the remaining subjects in Cohort A1 may be discharged from the study site after completion of all study procedures on Day 1, returning for subsequent procedures on an outpatient basis. For subsequent cohorts, the decision of when to discharge subjects from the study site will be made by the Investigator based on the safety data through Day 2 from the first 2 subjects of the current cohort, as well as any relevant recommendations made at the previous DMC dose escalation review meeting.

All subjects will return for a Safety Follow-up visit 7 (+3) days after dosing and an Additional Follow-up visit 14 ( $\pm$ 3) days after dosing. The timing of the Additional Follow-up visit for a cohort may be changed to a maximum of 28 ( $\pm$ 3) days after dosing, based on emerging safety data.

**Dose levels:**

Current proposed dose levels:

- Cohort A1: 2 mg
- Cohort A2: 10 mg
- Cohort A3: 30 mg
- Cohort A4: 60 mg

**Part B**

Part B will comprise a multiple-dose, single-period, sequential-cohort study. Potential subjects will be screened to assess their eligibility to enter the study within 28 days prior to initial study drug administration.

It is planned to study 18 subjects in 3 cohorts (Cohorts B1 to B3), each consisting of 6 subjects. Up to 3 further optional cohorts (Cohorts B4 to B6) of at least 6 subjects may be added to evaluate additional doses or to further evaluate planned doses.

**Investigational treatment and follow-up duration:**

After Screening, subjects will be dosed at the study site on Days 1, 8, 15, and 22. Subjects will return for a Safety Follow-up visit approximately 7 days after their last dose (Day 29 [+3]) and an Additional Follow-up visit approximately 14 days after the last dose (Day 36 [ $\pm$ 3]). The timing of the Additional Follow-up visit for a cohort may be changed to a maximum of approximately 28 days after the last dose (Day 50 [ $\pm$ 3]), based on emerging safety data.

**Dose levels:**

To be confirmed following completion of Part A. Current proposed dose levels:

- Cohort B1: 10 mg
- Cohort B2: 30 mg
- Cohort B3: 60 mg

**Number of subjects:**

Part A: 16 subjects will be studied in 4 groups (Groups A1 to A4), with the option to add up to 3 additional cohorts of at least 4 subjects at DMC recommendation.

Part B: 18 subjects will be studied in 3 groups (Groups B1 to B3), with the option to add up to 3 additional cohorts of at least 6 subjects at DMC recommendation.

**Diagnosis and main criteria for inclusion:**

Male and female subjects aged between 40 and 80 years (inclusive) with IPF. Subjects must have  $SpO_2 \geq 90\%$  at rest by pulse oximetry while breathing ambient air, FVC and  $FEV_1 \geq 50\%$  of predicted, ratio of  $FEV_1$  to FVC  $\geq 0.7$ , and  $DL_{CO}$  corrected for hemoglobin 30% to 79% of predicted, inclusive.

**Investigational products, dose, and mode of administration:**

Test product: [REDACTED] TRK-250 solution, formulated for inhalation via InnoSpire Go nebulizer system (Philips)

Proposed dose levels for Part A: 2, 10, 30, and 60 mg

Proposed dose levels for Part B: 10, 30, and 60 mg once weekly for 4 weeks. The dosing frequency and dosing duration for Part B will be decided on the basis of data from Part A of the study. The daily dose administered will not exceed the highest dose administered in Part A.

Administration route: inhalation

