**Figure 1: Study Schematic (Part A)**

**3.1.2. Part B**

Part B will comprise a multiple-dose, single-period, sequential-cohort study. Potential subjects will be screened to assess their eligibility to enter the study within 28 days prior to initial study drug administration.

The total duration of study participation for each subject (from Screening through Safety Follow-up visit) is planned to be no more than 10 weeks but may be increased to a maximum of 12 weeks if the Additional Follow-up visit is delayed based on findings from the ongoing review of data by the DMC.

[REDACTED]

[REDACTED]

[figure not shown]
All subjects will return for a Safety Follow-up visit approximately 7 days after their last dose (Day 29 [+3]) and an Additional Follow-up visit approximately 14 days after the last dose (Day 36 [ $\pm$ 3]). The timing of the Additional Follow-up visit for a cohort may be changed to a maximum of approximately 28 days after the last dose (Day 50 [ $\pm$ 3]), based on emerging safety data.

In each of Cohorts B1 to B3, 4 subjects will receive TRK-250 and 2 subjects will receive placebo. Doses will be administered on the morning of Days 1, 8, 15, and 22 in accordance with a randomization schedule. Each subject will receive 4 once-weekly doses of TRK-250 or placebo during the study. [REDACTED]

[REDACTED]

- Cohort B1: 10 mg
- Cohort B2: 30 mg
- Cohort B3: 60 mg

[REDACTED] shown in [Figure 2](#).

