**Table 4: Proposed IMP Dose Levels for Parts A and B**

Study Part	Cohort	Treatment
Part A	A1	2 mg TRK-250 or placebo
	A2	10 mg TRK-250 or placebo
	A3	30 mg TRK-250 or placebo
	A4	60 mg TRK-250 or placebo
	Optional Cohorts A5, A6, and A7	XX mg TRK-250 or placebo
Part B	B1	10 mg TRK-250 or placebo Q1W
	B2	30 mg TRK-250 or placebo Q1W
	B3	60 mg TRK-250 or placebo Q1W
	Optional Cohorts B4, B5, and B6	XX mg TRK-250 or placebo Q1W

Abbreviations: IMP = investigational medicinal product; Q1W = once weekly.

For Part B of the study, dose levels, dosing frequency, and dosing duration will be decided, in consultation with the Sponsor, on the basis of data from Part A of the study. The weekly dose of TRK-250 administered during this part of the study will not exceed the maximum well-tolerated dose level studied in Part A.

[REDACTED]

[REDACTED]

Details of all doses administered in Parts A and B of the study will be documented in the TMF.

[REDACTED]

[REDACTED]

[REDACTED]

[REDACTED]

[REDACTED]

[REDACTED]

[REDACTED]

[REDACTED]

[REDACTED]

[REDACTED]

[REDACTED]

| [REDACTED]

| [REDACTED]

[REDACTED]

[REDACTED]

[REDACTED]

[REDACTED]

| [REDACTED]

| [REDACTED]

| [REDACTED]

| [REDACTED]

| [REDACTED]

| [REDACTED]

| [REDACTED]

[REDACTED]

[REDACTED]

[REDACTED]

[REDACTED]

[REDACTED]

[REDACTED]

[REDACTED]

[REDACTED]

[REDACTED]

[REDACTED]

[REDACTED]

[REDACTED]

[REDACTED]

[REDACTED]

[REDACTED]

[REDACTED]

[REDACTED]

[REDACTED]

- | [REDACTED]
- | [REDACTED]
- | [REDACTED]
- | [REDACTED]

[REDACTED]

- | [REDACTED]
- | [REDACTED]
- | [REDACTED]
  - | [REDACTED]
  - | [REDACTED]
  - | [REDACTED]

[REDACTED]

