### 8.6. Interim Analysis

Between each dose escalation, the DMC will review all available safety data to ensure it is safe to proceed with the planned dose escalation, and also to make recommendations on the escalation to a higher exposure dosing regimen, progression to Part B, and dosing regimen to be used in Part B. Any clinically significant results will be discussed with the Sponsor before dose escalation continues. Interim PK data, where available, may also be reviewed in terms of dose escalation. These analyses will be performed with soft locked (not hard locked) data.

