**Table 2: Schedule of Assessments – Part B (Multiple Dose)**

Study Epoch	Screening	Treatment		Follow-up	
		Days 1, 8, 15 & 22 pre-dose	Days 1, 8, 15 & 22 dosing & post-dose	Safety Follow-up	Additional Follow-up
Study Day (Window)	-28 to -1	1, 8 (+1), 15 (+1) & 22 (+1) (≥7 days between doses)		29 (+3)	36 (±3)
Informed consent	X				
Inclusion/exclusion criteria	X	X			
Demographic data a	X				
Medical history	X	X b			
Body weight and height	X			X c	
Oral body temperature	X	X d	X	X	X
Blood pressure and pulse rate	X	X d	X e	X	X
SpO 2	X	X d	X e	X	X
Physical examination	X	X	X f	X f	X f
Pregnancy test g	X	Day 1 pre-dose only		X	
Follicle-stimulating hormone h	X				
12-lead ECG	X	X	X i	X	
HRCT	X j				
Spirometry k	X	X l	X l	X	X
Carbon monoxide diffusion capacity k	X	X d		X	X
Clinical chemistry and hematology	X	X		X	
Serology	X				
Urine drugs of abuse screen m	X				
[REDACTED]	■	■	■	■	■
Study treatment administration			X		
Adverse event recording		X	X	X	X
[REDACTED]					
Pharmacokinetic blood sampling		Days 1 & 22	Days 1 & 22 n		
[REDACTED]		■		■	■
[REDACTED]		■		■	■
[REDACTED]				■	■

Study Epoch	Screening	Treatment		Follow-up	
		Days 1, 8, 15 & 22 predose	Days 1, 8, 15 & 22 dosing & postdose	Safety Follow-up	Additional Follow-up
Study Procedures	Screening				
Study Day (Window)	-28 to -1	1, 8 (+1), 15 (+1) & 22 (+1) (≥7 days between doses)		29 (+3)	36 (±3)

Note, where multiple assessments are required at a single timepoint, the following order of procedures should be used: blood sampling, spirometry, other procedures (ECGs should be scheduled before vital signs measurements). See also footnote k.

Note, timing of safety and pharmacokinetic assessments may be changed based upon findings from previous cohorts.

Abbreviations: DLCO = carbon monoxide diffusion capacity; ECG = electrocardiogram; HRCT = high-resolution computed tomography; SpO2 = oxygen saturation.

a To include smoking history.

b Interim medical history.

c Height measured only at Screening.

d Within 60 minutes prior to dosing.

e 1 hour and 2 hours after completion of dose administration.

f Symptom-directed physical examination.

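### The protocol Synopsis and Section 3.5 set different ceilings for Part B dosing; at once weekly they agree only if the highest Part A dose was well tolerated

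*Protocol*

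**What the plan says.** The protocol's Synopsis, under investigational products, limits Part B as follows: "The daily dose administered will not exceed the highest dose administered in Part A". Section 3.5, in the text under Table 4, limits it differently: "The weekly dose of TRK-250 administered during this part of the study will not exceed the maximum well-tolerated dose level studied in Part A".

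On frequency, the Synopsis says "The dosing frequency and dosing duration for Part B will be decided on the basis of data from Part A of the study", and Section 3.5 likewise says that "dose levels, dosing frequency, and dosing duration will be decided, in consultation with the Sponsor, on the basis of data from Part A". The regimen actually written down is weekly. Section 3.1.2 says "Each subject will receive 4 once-weekly doses of TRK-250 or placebo during the study", Table 4 gives every Part B cohort (including the optional ones) a once-weekly schedule, and the Part B Schedule of Assessments in Appendix 5 requires "≥7 days between doses". SAP Section 7 also labels the three planned Part B treatments as weekly.

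Section 8.6 asks the data monitoring committee to "make recommendations on the escalation to a higher exposure dosing regimen, progression to Part B, and dosing regimen to be used in Part B".

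**The concern.** The two sentences limit the same thing, Part B dosing, and both are unconditional. They differ in two respects:

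- **Time unit.** The Synopsis limits the dose per day; Section 3.5 limits the dose per week.
- **Part A reference.** The Synopsis refers to the highest dose given, whether or not it was tolerated. Section 3.5 refers to the highest dose that was well tolerated.

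This is the stated upper limit for repeat dosing of a product not previously given to humans. The committee that recommends the Part B regimen has two statements of the limit before it. They separate in the situation for which a ceiling is written: a top Part A dose that was given but not well tolerated.

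**Working it through.** The plan gives no combined figure to reproduce, so the check compares the two rules directly.

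**Inputs**
- Part A levels, from the Synopsis: "Proposed dose levels for Part A: 2, 10, 30, and 60 mg".
- Proposed Part B levels, from the Synopsis and Table 4: 10, 30 and 60 mg once weekly.
- Notation: H is the highest dose given in Part A, M the highest Part A level that was well tolerated, d the Part B dose on a dosing day, and f the number of dosing days per week. By definition M ≤ H.

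**The two rules**
- Synopsis: d ≤ H, which allows at most f × H per week.
- Section 3.5: f × d ≤ M, which allows at most M per week.
- Ratio of the weekly ceilings: f × H / M.

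**Nesting.** If f × d ≤ M, then d ≤ f × d ≤ M ≤ H, so a regimen that meets Section 3.5 always meets the Synopsis. The converse fails whenever f × H > M.

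**Scheduled regimen, f = 1.** The daily and weekly doses are the same number, so the ceilings are simply H and M. They are equal only when H = M. The last three rows assume that H was not well tolerated and that M is the next lower planned level.

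| H (mg) | M (mg) | Synopsis ceiling (mg/week) | Section 3.5 ceiling (mg/week) | Ratio H / M |
|---|---|---|---|---|
| 60 | 60 | 60 | 60 | 1.0 |
| 60 | 30 | 60 | 30 | 2.0 |
| 30 | 10 | 30 | 10 | 3.0 |
| 10 | 2 | 10 | 2 | 5.0 |

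In each of the last three rows, the dose that the Synopsis sentence allows and the Section 3.5 sentence does not (60, 30 or 10 mg) is one of the proposed Part B doses. If M lay more than one level below H, the gap would be wider: 60/10 = 6-fold, 30/2 = 15-fold, 60/2 = 30-fold. H is also not fixed at 60 mg, because Section 3.3 lets optional cohorts go above the proposed top dose.

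**Other frequencies.** These are assumptions; the documents plan no such regimen. With H = M = 60 mg, so that tolerability plays no part:

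| f (days/week) | Synopsis, f × 60 (mg/week) | Section 3.5 (mg/week) | Ratio |
|---|---|---|---|
| 2 | 120 | 60 | 2.0 |
| 3 | 180 | 60 | 3.0 |
| 7 | 420 | 60 | 7.0 |

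All figures are nominal milligrams, not blood exposure.

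**The case against.** The strongest reply is that the rules do not collide. Both are firm limits, nothing presents them as alternatives, and they are nested. A reader who applies the whole protocol would obey both and so arrive at the Section 3.5 limit; the Synopsis sentence is then just a looser summary. This stands as far as it goes: the two can be met together, and the fault is an unreconciled inconsistency, not an impossible pair of rules. But the protocol never says that both apply or that one prevails, and a reader who relies on the Synopsis sees a ceiling with no tolerability condition.

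The time-unit difference has no effect at any regimen the documents schedule. A change of frequency would also contradict Section 3.1.2 and the Schedule of Assessments, and Appendix 4 requires approval of a protocol amendment before a design change takes effect. That is fair, and the 2-, 3- and 7-fold figures for other frequencies should carry little weight. They remain relevant only because both ceiling passages sit beside a clause that leaves frequency open. That clause is partly explained by Part B being provisional until Part A is complete.

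At once weekly the gap is conditional: it vanishes if the top Part A dose is well tolerated. The 2-, 3- and 5-fold figures illustrate the gap and are not a forecast.

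Finally, much of Sections 3.1.2, 3.4.1 and 3.5 is redacted, and Section 3.3 mentions escalation stopping criteria that cannot be seen. A definition of tolerability or a further limit may be there, and its absence from the public text is not counted against the plan. What can be seen is that the Synopsis sentence is unqualified and differs from the one in Section 3.5. Committee review before Part B lowers the practical risk but does not say which limit applies.

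**Conclusion.** The concern holds. The wording difference is certain: one limit on Part B dosing is stated in two ways, with different time units and different Part A references, and no visible text reconciles them. Its consequence for dose selection is conditional. At the scheduled once-weekly regimen there is no gap if the highest Part A dose was well tolerated. The gap is 2-, 3- or 5-fold if it was not and the next lower planned level was, using the planned dose levels. Redacted text may narrow the consequence. The point should be fixed because it concerns the repeat-dose ceiling in a first-in-human trial, but it affects no sample size, estimate or analysis. No view is taken here on which ceiling or which frequency is right.

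**What to change.** Reconcile the Synopsis sentence and the Section 3.5 sentence into one ceiling, with one time unit and one Part A reference quantity, worded identically in both places. In the same edit, reconcile the clauses in the Synopsis and Section 3.5 that leave dosing frequency open with the once-weekly regimen in Section 3.1.2 and the Part B Schedule of Assessments. The choice of ceiling and frequency rests with the sponsor and its clinical advisers.

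The cost is protocol wording, to be settled before any decision on the Part B regimen. It needs no extra subjects, visits or data.

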**Reference product and mode of administration:**

Reference product: placebo solution, formulated for inhalation via InnoSpire Go nebulizer system (Philips)

Administration route: inhalation

**Duration of subject participation in the study:**

Planned Screening duration: approximately 28 days.

Planned study duration (Screening to Follow-up):

Part A: planned to be no more than 7 weeks, but may be increased to a maximum of 9 weeks if the Additional Follow-up visit is delayed based on findings from the ongoing review of data by the DMC.

Part B: planned to be no more than 10 weeks, but may be increased to a maximum of 12 weeks if the Additional Follow-up visit is delayed based on findings from the ongoing review of data by the DMC.

**Analysis methods:****Pharmacokinetics:**

Blood samples for the analysis of TRK-250 concentrations. Pharmacokinetic parameters will be derived by noncompartmental analysis. For both study parts, the PK parameters will include  $AUC_{0-t_{last}}$ ,  $C_{max}$ , and  $T_{max}$ . Other PK parameters may also be added.

**Safety:**

AE, pulse oximetry, spirometry,  $DL_{CO}$ , body weight, clinical laboratory evaluations (hematology, clinical chemistry, urinalysis, serology), 12-lead electrocardiograms, vital sign measurements, and physical examinations.

**Statistical methods:****Pharmacokinetics:**

Individual blood concentrations of TRK-250 and PK parameters will be listed and summarized using descriptive statistics.

**Safety:**

Safety parameters will be listed and summarized using descriptive statistics. No inferential statistical analysis of safety data is planned.

**LIST OF ABBREVIATIONS**

Abbreviation	Definition
ABCA3	adenosine triphosphate binding cassette A3
AE	adverse event(s)
ALAT	Latin American Thoracic Association
ALT	alanine aminotransferase
AST	aspartate aminotransferase
ATS	American Thoracic Society
AUC	area under the concentration-time curve
AUC 0-24h	area under the concentration-time curve from time 0 to 24 hours
AUC 0-tlast	area under the concentration-time curve from time zero to the time of the last quantifiable concentration
[REDACTED]	[REDACTED]
[REDACTED]	[REDACTED]
CFR	Code of Federal Regulations
CIOMS	Council for International Organizations of Medical Sciences
C max	maximum observed concentration
CRF	Case Report Form(s)
CRO	Contract Research Organization
CSA	clinical study agreement
DL CO	carbon monoxide diffusion capacity
DMC	data monitoring committee
ECG	electrocardiogram
EDC	electronic data capture
ERS	European Respiratory Society
FDA	Food and Drug Administration
FEV 1	forced expiratory volume over 1 second
FLP	full length product
FVC	forced vital capacity
FVC%pred	percent of predicted forced vital capacity
GCP	Good Clinical Practice
GLI	Global Lung Initiative
GLP	Good Laboratory Practice
HEPA	high efficiency particulate air
HRCT	high-resolution computed tomography
IB	Investigator's Brochure
IC 50	concentration that reduces effect by 50%
ICF	Informed Consent Form

ICH	International Council for Harmonisation
IMP	investigational medicinal product
IPF	idiopathic pulmonary fibrosis
IRB	Institutional Review Board
IUD	intrauterine device
IxRS	interactive voice/web response system
JRS	Japanese Respiratory Society
LC-FD	liquid chromatography with fluorescence detection
LC/MS-HRAM	liquid chromatography/mass spectrometry-high resolution accurate mass
LLOQ	lower limit of quantification
MABEL	minimum anticipated biological effect level
MedDRA	Medical Dictionary for Regulatory Activities
██████	████████████████████
██████	████████████████████
██████	████████████████████
mRNA	messenger ribonucleic acid
██████	████████
NOAEL	no-observed-adverse-effect level
██████	████████████████████
PK	pharmacokinetic(s)
QTcB	QT interval corrected for heart rate using Bazett's method
QTcF	QT interval corrected for heart rate using Fridericia's method
SAE	serious adverse event
siRNA	small, interfering ribonucleic acid
SLB	surgical lung biopsy(ies)
SOP	standard operating procedure(s)
SP-A2	surfactant protein A2
SP-C	surfactant protein C
SpO 2	oxygen saturation
TGF-β1	transforming growth factor-beta 1
T max	time of maximum observed concentration
TMF	Trial Master File
UIP	usual interstitial pneumonia
ULN	upper limit of normal
WCBP	women of childbearing potential

## 1. INTRODUCTION

### 1.1. Overview

Interstitial pulmonary fibrosis (IPF) is one of the interstitial pneumonias, known also as cryptogenic fibrosing alveolitis. The condition is also identified as usual interstitial pneumonia (UIP), the term given its appearance on high-resolution computed tomography (HRCT) scans of the lung and histopathologic examination of surgical lung biopsies (SLB).

Toray Industries, Inc. (Toray), is developing TRK-250 for the potential treatment of IPF.

An international, professional society (American Thoracic Society/European Respiratory Society/Japanese Respiratory Society/Latin American Thoracic Association [ATS/ERS/JRS/ALAT]) statement defines IPF as a specific lung disorder of adults, of unknown cause, characterized by progressive dyspnea, associated with poor prognosis, resulting from progressive fibrosing interstitial pneumonia of unknown cause. Criteria for the diagnosis of IPF detailed in this publication are adopted as criteria central to establishing subject eligibility for this clinical trial.

The etiology of IPF remains undetermined. Risk factors have been identified, including:

- cigarette smoking and atmospheric pollutants
- viral infection
- chronic aspiration
- drugs

Genetic predisposition seems to play a role in some cases of IPF. Mutations in surfactant proteins A2 (SP-A2) and C (SP-C) as well as in adenosine triphosphate binding cassette A3 (ABCA3) genes appear to be involved in cases of familial IPF. A genetic abnormality in the promoter of the gene encoding mucin 5B (MUC5B) has been identified in about one third of individuals with familial and sporadic IPF; the abnormality is only found in about 9% of individuals without clinical evidence of IPF. Telomerase gene mutations (TERT, TERC, DKC1, TINF2) that cause shortened telomeres have been identified in about one quarter of sporadic and more than one third of familial IPF cases. Still, the interplay of all risk factors remains poorly understood, more so in sporadic IPF cases.

A central role for transforming growth factor-beta 1 (TGF-β1) has been documented for decades in fibrosis in many organs, in airway remodeling, and in IPF. TRK-250 is a small, interfering ribonucleic acid (siRNA) molecule that targets the TGF-β1 guide sequence. TRK-250 aims to inhibit the progression of pulmonary fibrosis and, thus, slow the decline in lung function, by selectively targeting TGF-β1 messenger ribonucleic acid (mRNA) and thereby suppressing the expression of TGF-β1 protein, a key growth factor involved in lung fibrosis, at the gene expression level. TRK-250 employs a proprietary nucleic acid platform that synthesizes 2 complementary single oligoribonucleotide strands. The 2 strands of oligoribonucleotides are linked by a proline derivative and a second proline derivative terminated with guanine completes the sequence. TRK-250 is formulated as a solution for inhalation, supporting direct administration to the lung.

This trial will be the first time that TRK-250 is administered to humans.

[REDACTED]

[REDACTED]

[REDACTED]

[REDACTED]

[REDACTED]

[REDACTED]

[REDACTED]

[REDACTED]

[REDACTED]

[REDACTED]

[REDACTED]

[REDACTED]

[REDACTED]

[REDACTED]

[REDACTED]

[REDACTED]

[REDACTED]

[Redacted]

[Redacted]

[Redacted]

[Redacted]

[Redacted]

[Redacted]	[Redacted]	[Redacted]	[Redacted]	[Redacted]	[Redacted]	[Redacted]	[Redacted]	[Redacted]	[Redacted]	[Redacted]	[Redacted]	[Redacted]	[Redacted]	[Redacted]	[Redacted]	[Redacted]	[Redacted]	[Redacted]	[Redacted]	[Redacted]
[Redacted]	[Redacted]	[Redacted]	[Redacted]	[Redacted]	[Redacted]	[Redacted]	[Redacted]	[Redacted]	[Redacted]	[Redacted]	[Redacted]	[Redacted]	[Redacted]	[Redacted]	[Redacted]	[Redacted]	[Redacted]	[Redacted]	[Redacted]	[Redacted]
[Redacted]	[Redacted]	[Redacted]	[Redacted]	[Redacted]	[Redacted]	[Redacted]	[Redacted]	[Redacted]	[Redacted]	[Redacted]	[Redacted]	[Redacted]	[Redacted]	[Redacted]	[Redacted]	[Redacted]	[Redacted]	[Redacted]	[Redacted]	[Redacted]
[Redacted]	[Redacted]	[Redacted]	[Redacted]	[Redacted]	[Redacted]	[Redacted]	[Redacted]	[Redacted]	[Redacted]	[Redacted]	[Redacted]	[Redacted]	[Redacted]	[Redacted]	[Redacted]	[Redacted]	[Redacted]	[Redacted]	[Redacted]	[Redacted]

[Redacted]

[REDACTED]

[REDACTED]	[REDACTED]	[REDACTED]	[REDACTED]	[REDACTED]	[REDACTED]	[REDACTED]	[REDACTED]	[REDACTED]	[REDACTED]	[REDACTED]	[REDACTED]	[REDACTED]	[REDACTED]	[REDACTED]	[REDACTED]
[REDACTED]	[REDACTED]	[REDACTED]	[REDACTED]	[REDACTED]	[REDACTED]	[REDACTED]	[REDACTED]	[REDACTED]	[REDACTED]	[REDACTED]	[REDACTED]	[REDACTED]	[REDACTED]	[REDACTED]	[REDACTED]
[REDACTED]	[REDACTED]	[REDACTED]	[REDACTED]	[REDACTED]	[REDACTED]	[REDACTED]	[REDACTED]	[REDACTED]	[REDACTED]	[REDACTED]	[REDACTED]	[REDACTED]	[REDACTED]	[REDACTED]	[REDACTED]
[REDACTED]	[REDACTED]	[REDACTED]	[REDACTED]	[REDACTED]	[REDACTED]	[REDACTED]	[REDACTED]	[REDACTED]	[REDACTED]	[REDACTED]	[REDACTED]	[REDACTED]	[REDACTED]	[REDACTED]	[REDACTED]

[REDACTED]

[REDACTED]	[REDACTED]	[REDACTED]	[REDACTED]	[REDACTED]	[REDACTED]	[REDACTED]	[REDACTED]	[REDACTED]	[REDACTED]	[REDACTED]	[REDACTED]	[REDACTED]	[REDACTED]	[REDACTED]	[REDACTED]
[REDACTED]	[REDACTED]	[REDACTED]	[REDACTED]	[REDACTED]	[REDACTED]	[REDACTED]	[REDACTED]	[REDACTED]	[REDACTED]	[REDACTED]	[REDACTED]	[REDACTED]	[REDACTED]	[REDACTED]	[REDACTED]
[REDACTED]	[REDACTED]	[REDACTED]	[REDACTED]	[REDACTED]	[REDACTED]	[REDACTED]	[REDACTED]	[REDACTED]	[REDACTED]	[REDACTED]	[REDACTED]	[REDACTED]	[REDACTED]	[REDACTED]	[REDACTED]
[REDACTED]	[REDACTED]	[REDACTED]	[REDACTED]	[REDACTED]	[REDACTED]	[REDACTED]	[REDACTED]	[REDACTED]	[REDACTED]	[REDACTED]	[REDACTED]	[REDACTED]	[REDACTED]	[REDACTED]	[REDACTED]

[REDACTED]

